15.2. Sample Size Determination

The sample size calculation for this study will be based on parameters derived from previous DIALOG+ trials (35). A standard deviation of 0.9 for the MANSA and a correlation of 0.4 between baseline and follow-up measurements will be assumed, while an effect size of 0.4 points on the MANSA will be considered the minimal clinically important difference (MCID) for quality of life in this patient population. Based on these parameters, a total of 90 participants per group will be required to achieve 90% power at the 5% two-sided significance level. To account for an anticipated 20% attrition rate, the final sample size will be set at 226 participants (113 per group).

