12.7. Randomisation

The unit of randomisation will be the individual participant. Site-stratified blocked randomisation, with a variable block size ranging from two to four, will be performed on a rolling basis during the recruitment period. A randomisation schedule will be defined for each health centre (study site). Within each stratum, participants will be randomised in a 1:1 ratio to either DD+ or the control group. Randomisation will be performed using REDCap or via a phone call, following the corresponding randomisation schedule.

Figure 3. Study Randomisation Summary

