13.3.3. Dynamic DIALOG+ providers

Up to two DD+ previously trained providers per region (Bogotá, Cauca, Guaviare, Amazonas) will be invited to participate.

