15.7. Primary Objective

The primary outcome data (MANSA scores) will be summarised at baseline and 6 months. At each time point, the number of observations, means, and standard deviations will be reported separately for the intervention and control groups to support interpretation of changes over time.

A mixed-effects linear regression model will be used to evaluate the effect of the intervention on MANSA scores at 6 months. Fixed effects will include treatment group (intervention vs control) and the baseline MANSA score to adjust for initial differences. Clinician or healthcare practitioners clusters will be modelled as a random effect to account for intra-cluster correlation.

The model will estimate the adjusted mean difference in MANSA scores between the two groups, with corresponding 95% confidence intervals (CIs) and p-values.

Formally, the model can be expressed as:

$$y = X\beta + Z\gamma + \varepsilon$$

y is the vector of observed MANSA scores, X is the design matrix for fixed effects, β is the vector of fixed-effect parameters (including the treatment group and baseline MANSA), $Z\gamma$ represents the random effects, with Z being the design matrix for random effects and γ the corresponding random-effect parameters (clinician clusters) and ε is the vector of residual errors.

In lay terms:

Mixed-effects model = Fixed effects (treatment arm + covariates) + Random effects (clinician clusters). The mixed-effects model accounts for both fixed effects—such as treatment group and relevant covariates—and random effects arising from the clustering of participants within clinicians.

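### Section 15.2's 90% power holds only if patients of the same DD+ deliverer are essentially uncorrelated, although section 15.7 models that correlation

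*Protocol*

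**What the plan says.** Section 15.2 sets the inputs: "A standard deviation of 0.9 for the MANSA and a correlation of 0.4 between baseline and follow-up measurements will be assumed". The target difference is 0.4 MANSA points. From these, "a total of 90 participants per group will be required to achieve 90% power at the 5% two-sided significance level", and 20% attrition raises this to 113 per group, 226 in all. The section mentions no ICC, caseload, number of clinicians or design effect.

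Section 12.7 randomises individuals 1:1 within site: "The unit of randomisation will be the individual participant".

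Section 15.7 specifies the primary model as a mixed-effects regression on treatment and baseline MANSA, in which "Clinician or healthcare practitioners clusters will be modelled as a random effect to account for intra-cluster correlation". Section 15.9 uses the same structure for the secondary outcomes.

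Sections 6, 10.1 and 12.9 have DD+ delivered by contracted, trained trial staff in dedicated monthly appointments. Section 16 adds that the trial clinician is not part of the patient's care team. The only count of providers is in section 13.3.3: "Up to two DD+ previously trained providers per region (Bogotá, Cauca, Guaviare, Amazonas) will be invited to participate". That sentence concerns the implementation assessment.

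**The concern.** The sample size treats all participants as independent, while the primary analysis expects outcomes to be correlated within clinician. Individual randomisation does not settle this. After allocation, DD+ participants share a deliverer over six sessions and control participants have none. If deliverers differ in their effect, the DD+ mean carries extra variance that 15.2 does not count.

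At stake is the 90% figure itself. It is presented as a property of the design, and readers will use it when judging whether a null result speaks against a 0.4-point effect. The source cited for the planning parameters is listed in the references as the protocol of a cluster-randomised DIALOG+ trial, so clustering was a feature of the parent design, yet no ICC is stated here.

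**Working it through.** **Inputs from section 15.2:** SD 0.9, correlation 0.4, difference 0.4, two-sided 5%, 90% power, 20% attrition.

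**Step 1: reproduce the plan.**
- Baseline-adjusted variance: 0.81 × (1 − 0.16) = 0.6804 (SD 0.825).
- n per arm = 2 × (1.960 + 1.2816)² × 0.6804 / 0.16 = 89.37, rounded up to 90.
- Attrition: 90 / 0.8 = 112.5, rounded up to 113.
- The alternatives do not give 90: an unadjusted comparison needs 107 and a change score 128.
- Power at 90 per arm: SE = √(2 × 0.6804 / 90) = 0.1230; Φ(0.4/0.1230 − 1.96) = 90.2%.

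The plan's figure is thus an ANCOVA size with a design effect of exactly 1 and 0.2 points of power in reserve.

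**Step 2: how much clustering the reserve absorbs.** Let k deliverers share the 90 analysed DD+ participants, so m = 90/k, and leave controls unclustered:
- DE = 1 + (m − 1) × ICC
- SE² = 0.6804 × (DE + 1) / 90

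Power of 90% needs SE² ≤ (0.4 / 3.2416)² = 0.01523. Then DE + 1 ≤ 0.01523 × 90 / 0.6804 = 2.014, so DE ≤ 1.014. That is an ICC of about 0.014/10.25 = 0.0014 with 8 deliverers, or 0.014/5 = 0.0028 with 15.

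**Step 3: power over a range.** Both k and the ICC are assumptions. The value 8 is two per region in four regions (section 13.3.3, an implementation-assessment sample). The value 15 is the number of centres in section 15.11.4. Power = Φ(0.4/SE − 1.96).

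| Deliverers | m | ICC | DE | SE | Power |
|---|---|---|---|---|---|
| 15 | 6 | 0.01 | 1.050 | 0.1245 | 89.5% |
| 15 | 6 | 0.05 | 1.250 | 0.1304 | 86.6% |
| 15 | 6 | 0.10 | 1.500 | 0.1375 | 82.9% |
| 8 | 11.25 | 0.01 | 1.103 | 0.1261 | 88.7% |
| 8 | 11.25 | 0.05 | 1.513 | 0.1378 | 82.7% |
| 8 | 11.25 | 0.10 | 2.025 | 0.1512 | 75.3% |

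**Step 4: few clusters.** The normal approximation flatters these figures. For 8 deliverers at ICC 0.05, Satterthwaite degrees of freedom are (1.5125 + 1)² / (1.5125²/7 + 1²/89) = 18.7, and a noncentral t calculation gives about 79% in place of 82.7%.

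**The case against.** The strongest reply is that the protocol never says the cluster is the DD+ deliverer. Section 15.7 speaks of clinicians or practitioners, section 15.9 of a professional group, and section 15.4 puts clinician in the imputation model without limiting it to one arm. Only the cost model in section 15.11.7 names the practitioners who delivered the intervention. If the cluster were a care team seen by both arms, site-stratified individual randomisation would make clusters cross the arms. The variance factor would then be about 1 − ICC, and power would rise: at ICC 0.05, SE = √(2 × 0.6804 × 0.95 / 90) = 0.1199 and power is 91.6%. It stands that the cluster definition is open and needs fixing. It does not remove the problem, because control participants have no DD+ deliverer, so any deliverer effect sits in one arm whichever cluster the model names.

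Site differences are a further fair point. Stratification balances them between arms, so only variation between deliverers within a site inflates the contrast. A published ICC that mixes the two would overstate the loss.

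Three stronger readings are tempting, and the documents do not support them:
- **That the calculation is wrong.** It is right on its own inputs; an input was left out.
- **That eight clinicians deliver DD+.** Section 13.3.3 caps invitations to the implementation assessment. The number of deliverers is nowhere stated.
- **That 113 per arm certainly misses 90%, or that the trial is badly underpowered.** With zero deliverer ICC the plan delivers its 90%, and at small ICCs power stays above 80%. Applying a cluster-trial design effect to both arms would exaggerate the loss: 75.3% in place of 82.7% at ICC 0.05 with 8 deliverers.

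A null result would also be read against the confidence interval from the clustered model. That limits the harm but does not correct the stated power.

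**Conclusion.** The power statement is wrong as written. It is unconditional, but it holds only if the correlation between patients of the same DD+ deliverer is essentially zero, which conflicts with the correlation that section 15.7 sets out to model.

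The omission is certain; the size of the shortfall is not. Over the assumed range it runs from under 1 point (15 deliverers, ICC 0.01) to about 15 points (8 deliverers, ICC 0.10), before any loss from few degrees of freedom. These figures assume equal caseloads, 90 analysed per arm and clustering in the DD+ arm only.

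**What to change.** Keep 226 participants.

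- **Section 15.2:** say that 90% power assumes no correlation within DD+ deliverer. Give the planned number of deliverers and expected caseload, an assumed ICC range with its source, and the power from a partially nested formula that allows for few clusters.
- **Section 15.7:** state that the cluster is the DD+ deliverer and that control participants enter as unclustered. Align the cluster wording in section 15.9.

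The cost is a less favourable power statement and a short text amendment. No extra patients, visits or changes to conduct are needed.

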15.3. Analysis populations

The primary and Secondary (Effectiveness) analysis will follow the intention-to-treat (ITT) principle, including all randomised participants in the groups to which they were originally allocated, regardless of treatment received, adherence, or withdrawal. Participants who discontinue or deviate from the intervention will remain in their assigned group for analysis (49). Missing data will be imputed as specified in the following subsection.

15.4. Procedure for Accounting for Missing, Unused, and Spurious Data.

For the primary and secondary analysis of the outcome and in line with the intention-to-treat (ITT) principle, missing data will be addressed using multiple imputation by chained equations (MICE) (50). The imputation model will incorporate treatment group and relevant baseline covariates including study clinician age, sex, clinician, and baseline MANSA score or other measures that are relevant according to the objective of the analysis. The imputation will be conducted under the assumption that data are missing at random (MAR). Rubin's rules (51) will be applied to pool the estimates across multiple imputed datasets, thereby reflecting the uncertainty associated with the imputation process. This approach aims to preserve the structure of the data and reduce bias due to missingness.

A sensitivity analysis will be conducted to assess the impact of missing data assumptions, comparing multiple imputation estimates with those from a complete-case analysis.

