15.11.6. Analysis of population and missing data

The economic analysis set will include all randomised participants, in line with the intention-to-treat (ITT) principle. Missing data on costs and other outcome variables in the health economic analysis will be examined. Mean imputation and multiple imputation methods will be applied to address missing data.

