16. STUDY LIMITATIONS AND BIAS CONTROL

Due to the diversity of settings in terms of geographic location and sociodemographic characteristics, the risk of bias due to lack of representativeness of the Colombian population will be low. The randomisation procedure is also expected to generate balanced groups, reducing the risk of differential selection bias and minimising the chances of differential losses. However, since participants in the control group will have less contact with the study team and will be aware of their allocation due to unblinding, there is a risk of higher losses in this group. To mitigate this, routine phone calls will be made to control participants as reminders for the 6- and 12-month follow-up assessments.

A risk of contamination bias exists due to the public availability of the DIALOG+ application in the Play Store. However, for the active group, the intervention will be delivered by a trial clinician in the intervention appointments. In contrast, the follow-up visits for the control group will be through brief phone calls. Neither the trial clinician nor the researcher in charge of the follow-up call will be part of the patient care team. Furthermore, the fact that the application is publicly available will not be explicitly disclosed to participants to minimise the risk of bias.

The lack of blinding may also introduce bias through QoL outcome overestimation. However, outcome assessors and statisticians will remain blinded to allocation to reduce the risk of overestimating the effect or its magnitude. The risk of allocation concealment failure exists, but it is limited because the allocation will be automatically provided by the REDCap platform and only disclosed at the end of the baseline assessment visit.

A risk of outcome misclassification also exists. Although the diagnostic scales and tests used are validated and widely applied, the absence of measurement errors cannot be guaranteed. However, any misclassification is not expected to be differential. Finally, the risk of confounding is low due to randomisation, but not negligible. Therefore, statistical analyses for primary and secondary outcomes will adjust for relevant covariates, and the interpretation of results will consider the distribution of known variables among intervention and control groups.

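### Section 15.4's check on missing-data assumptions never departs from MAR, and Section 15.11.6 does not confine mean imputation to baseline covariates

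*Protocol*

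**What the plan says.** **Clinical outcomes (Protocol 15.4).** For the primary and secondary outcomes, "missing data will be addressed using multiple imputation by chained equations (MICE"), and "The imputation will be conducted under the assumption that data are missing at random (MAR"). On predictors: "The imputation model will incorporate treatment group and relevant baseline covariates including study clinician age, sex, clinician, and baseline MANSA score", with room for other measures relevant to the objective. No post-baseline predictor is named. One sensitivity analysis is given: "A sensitivity analysis will be conducted to assess the impact of missing data assumptions, comparing multiple imputation estimates with those from a complete-case analysis".

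**Primary model (Protocol 15.7).** "Fixed effects will include treatment group (intervention vs control) and the baseline MANSA score to adjust for initial differences". Clinician enters as a random effect.

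**Loss to follow-up (Protocol 16).** Because controls have less contact with the team and know their allocation, "there is a risk of higher losses in this group". The response is: "To mitigate this, routine phone calls will be made to control participants as reminders for the 6- and 12-month follow-up assessments". Section 15.2 assumes 20% attrition overall and gives no figure by arm.

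**Economic outcomes (Protocol 15.11.6).** For missing costs and other outcome variables: "Mean imputation and multiple imputation methods will be applied to address missing data". The section does not say which variable gets which method, which method is the base case, or which mean is meant. Section 15.11.8 then expresses sampling uncertainty through cost-effectiveness planes and acceptability curves.

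**The concern.** A sensitivity analysis of a missing-data assumption has to vary that assumption. Complete-case analysis is often labelled MCAR. In a model adjusted for arm and baseline MANSA, however, it is valid whenever loss depends only on those covariates. Multiple imputation relaxes this slightly, by letting loss also depend on the extra imputation predictors. Neither analysis allows loss to depend on the 6-month MANSA itself. If controls who know their allocation leave partly because of how they are doing, both estimates are biased together, and their agreement would be read as robustness.

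In the economic analysis, filling missing follow-up costs or utilities with a mean adds observations that carry no residual variation. Depending on which mean is used, this either understates the standard error or pulls the arms together. Both carry through to the incremental cost, the incremental QALY, the planes and the acceptability curves.

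**Working it through.** **Inputs.** From Section 15.2: SD 0.9, baseline to follow-up correlation 0.4, target difference 0.4, 90% power, two-sided 5%, 20% attrition, 113 per group. Assumed, because the document gives no such figures: loss by arm, the size of any departure from MAR, and the fraction of missing economic data.

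**1. The plan's own figure.** The ANCOVA-adjusted SD is 0.9 × √(1 − 0.4²) = 0.825. Then n = 2 × [0.825 × (1.960 + 1.282)/0.4]² = 89.4, rounded up to 90 per group. 90/0.8 = 112.5, rounded up to 113, total 226. The sample size reproduces and is not at issue.

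**2. What the comparison can and cannot see.** In a simulation of 1,000 trials (113 per arm, true effect 0.40, loss set near 25% control and 15% DD+, 20 imputations from arm and baseline MANSA, no clinician effect), average estimates were:

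| Loss mechanism (assumed) | Complete-case | Multiple imputation |
|---|---|---|
| MAR | 0.397 | 0.397 |
| Moderate outcome-dependent loss | 0.568 | 0.568 |
| Strong outcome-dependent loss | 0.735 | 0.735 |

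The mean absolute gap between the two analyses was about 0.01 in every row, whether the bias was nil, 0.17 or 0.33. In this simulation the imputation model had the same covariates as the analysis model. When an assumed prognostic baseline variable, used for imputation but absent from the primary model, drove control loss, complete-case averaged 0.47 and imputation 0.40, a mean gap of 0.07. So the comparison does respond to omitted predictors. It does not respond to loss driven by the unseen outcome.

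**3. Possible size of a departure from MAR.** Let dD and dC be the amounts by which missing DD+ and control patients differ from their MAR predictions. The true difference minus the MAR estimate is (DD+ loss) × dD − (control loss) × dC. At 15% and 25% loss:

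- Both arms +0.4: 0.15 × 0.4 − 0.25 × 0.4 = −0.04 (10% of the target).
- Controls only, +0.4: −0.25 × 0.4 = −0.10 (25%).
- DD+ −0.4 and controls +0.4: −0.06 − 0.10 = −0.16 (40%).

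Reversing the signs gives the same sizes upward. The last figure is the corner of the assumed range, and it is also 0.16 at 20%/20% and at 30%/10% loss.

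**4. Mean imputation of a follow-up outcome, 113 per arm, 20% missing (90.4 observed), simple two-arm comparison.**

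- *Arm mean.* The point estimate is unchanged. The SE relative to its proper value is √(89.4/112) × √(90.4/113) = 0.893 × 0.894 = 0.80. Type I error is 2 × [1 − Φ(1.96 × 0.799)] = 11.7%, and coverage is 88.3%. At 10% missing, type I error is 7.8%; at 30%, it is 17.1%.
- *Overall mean.* The difference and its SE both shrink by about 0.80, so type I error stays near 5%. A true difference of 0.40 becomes 0.32. With SD 0.9, the bias of −0.08 against an SE of about 0.107 gives coverage Φ(2.71) − Φ(−1.21) ≈ 88%. This loss of coverage grows with the true difference and vanishes when the difference is zero.

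**The case against.** The strongest reply has four parts.

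- *Delta-adjusted and tipping-point analyses commonly sit in the statistical analysis plan, which is not at hand.* This stands as far as their absence goes. It does not rescue the protocol's own statement that imputation against complete cases assesses the impact of the assumptions, and that statement is the point made here.
- *The two analyses are not bound to agree.* This also stands. A reader might infer that they match by construction, but Section 15.4 gives the imputation model age, sex and possibly other measures that the primary model lacks. Step 2 shows that such predictors can separate the results. What remains is that no departure from MAR is examined.
- *Section 16 does not predict excess control loss.* Correct. It states a risk, expects randomisation to limit differential loss, and plans reminder calls; Section 15.6 reports missingness by arm. Unequal loss is also not in itself a breach of MAR, because arm is in the imputation model. The concern is the stated mechanism, awareness of allocation and less contact, which makes outcome-related loss plausible without establishing it.
- *Section 15.11.6 may intend mean imputation only for baseline values.* Baseline utility and baseline cost are covariates in Section 15.11.7, so that split is possible. But the sentence concerns costs and outcome variables and sets no such limit. A reader might infer that the economic intervals will be too narrow, or that type I error will be 11.7%. The text supports neither as a certainty: the first needs arm-mean imputation of follow-up values, and the second also needs a simple comparison rather than the planned cost models and acceptability curves.

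**Conclusion.** The concern holds in two limited parts.

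First, the sensitivity analysis in Section 15.4 is described more broadly than it can deliver. It can show the influence of additional imputation predictors; it cannot show the effect of loss that depends on the unseen 6-month MANSA. Under the assumed 25%/15% loss and departures of 0.4 points, that effect runs from 0.04 (same direction in both arms) through 0.10 (controls only) to 0.16 (opposite directions). The largest figure is a worst case that does not depend on loss being unequal, and should not be read as a likely bias.

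Second, Section 15.11.6 leaves mean imputation open for follow-up costs and utilities. At an assumed 20% missing, arm means would give an SE about 0.80 of its proper value; the overall mean would shrink the difference by about 20%. Coverage would be about 88% either way, in the second case for a difference of 0.40 with SD 0.9. Either would distort the cost-effectiveness planes and acceptability curves. This is conditional on that use, which the text permits but does not fix.

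The choice of multiple imputation as primary is sound.

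**What to change.** **Section 15.4.** Keep multiple imputation under MAR as primary. Add delta-adjusted (pattern-mixture) multiple imputation with separate shifts for each arm, for example from −0.4 to +0.4 MANSA points, and report the tipping point at which the conclusion changes. Keep complete-case analysis as supplementary, described as showing the influence of the imputation predictors.

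**Section 15.11.6.** Impute follow-up costs and utilities by multiple imputation, jointly and by arm. Restrict mean imputation to missing baseline covariates, and state which method is the base case.

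**Cost.** A few sentences of text and a little more analysis work in R. No extra data or patients, and no change to the sample size. Both changes should be fixed before unblinded outcome data are seen.
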